**a. Position of the Investigator:**

Faculty or Non-Academic Equivalent  
 Student  
 Staff  
 Resident/Fellow  
 Other

**4. What type of application is being submitted?**

New Study Application (or Amendment/Continuing Review)

**5. Title Of Study:**

70 versus 110 Degrees Side-cut Angles in Femtosecond Laser-assisted in situ Keratomileusis

**6. Study Purposes and Objectives:**

Different side-cut angles have been used in Femtosecond Laser-assisted in Situ Keratomileusis (FS-LASIK), but no study has compared the safety and efficacy of 70 and 110 degrees side-cut angles. We aim to conduct a prospective trial comparing 70 and 110 degrees side-cut angles on same patient undergoing FS-LASIK. One angle will be performed on the right eye and the other on the left eye. The study will evaluate uncorrected visual acuity, best corrected visual acuity, intraoperative, and postoperative complications. By performing different side-cut angles on a same individual will allow a direct comparison of outcomes, minimizing confounding variables. Additionally, the LASIK flap will be performed using either the Abbott Medical Optics Intralase femtosecond laser or the Alcon Wavelight FS200 femtosecond laser.

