 **Experimental and/or Interventional Research Design:**

Prospective Biomedical Intervention or Experiment  
Randomized Trial

 **Development of a research resource (repositories, databases, etc.)** **Other****2. Does your study involve the use of any placebo?** Yes  No**3. Length of entire study, from initiation through closeout:**

2 years

**4. How will participants be recruited or identified for inclusion in the study?****a. Select all methods that will be used:**

In-person contact (e.g., patients, students, etc.)

Written advertising (flyers, brochures, website postings, newspaper ads, etc.)

Other

Information will be included on the moran eye center website, moran eye center facebook, and moran eye center twitter account.

[http://healthcare.utah.edu/moran/patient\\_care/refractive\\_surgery\\_lasik/](http://healthcare.utah.edu/moran/patient_care/refractive_surgery_lasik/)

<https://www.facebook.com/moraneyecenter>

<https://twitter.com/MoranEyeCenter>

**b. Describe the recruitment/participant identification process in detail (e.g. who will review charts or records, who can refer participants to the study, where will flyers be posted, how often will recruitment letters be sent, when will follow-up phone calls be made, etc.):**

When patients come in requesting refractive surgery, they are asked if they would like to participate in the study. An advertisement will be included on the Moran Eye Center website, facebook page, and twitter account, as well as in newsprint.

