**5. How will consent be obtained?**

Informed Consent Process (with or without a document)

**6. Describe all the procedures chronologically, from screening/enrollment through study closeout, which will be completed in the research project.**

Patients who are interested and eligible to participate in this study will sign the study informed consent prior to surgery. As is standard for our LASIK cases, they will also be required to watch an informational video, read and sign the "Consent to Have Refractive Surgery" and respond to a brief test concerning its content.

All surgical procedures will be performed according to the surgeons' standard practices. The study outcome measures are standard of care for pre-operative and post-operative evaluation of refractive surgery patients.

All study outcome measures will be evaluated for both eyes at every visit. Patient will be masked as to the treatment they receive in either eye so as not to influence their subjective responses and visual measurements. Post-operative evaluations will be performed at 1 day, 1 week ( $\pm$  3 days), 1 month ( $\pm$  10 days), 3 months ( $\pm$  14 days), 6 months ( $\pm$  1 month), and 12 months ( $\pm$  1 month). Interim examinations may be performed as necessary according to the surgeon's usual care, but are not considered part of the study data.

Patients will be discontinued from the study if, on the day of surgery, both eyes cannot be randomized and operated as per protocol. Patients have the right to withdraw at any time and future medical care will not be influenced by their lack of participation.

Patients will be evaluated with the following procedures:

- Manifest refraction (sphere, cylinder and axis): Pre op and post-op months 1 ( $\pm$  10 days), 3 ( $\pm$  14 days), 6 ( $\pm$  1 month), and 12 ( $\pm$  1 month).
- Uncorrected corrected visual acuity: Pre-op and post-op day 1, week 1, and months 1 ( $\pm$  10 days), 3 ( $\pm$  14 days), 6 ( $\pm$  1 month), and 12 ( $\pm$  1 month) using the Snellen Eye chart
- Best corrected visual acuity: Pre-op and post-op months 3 ( $\pm$  14 days), 6 ( $\pm$  1 month), and 12 ( $\pm$  1 month).
- Pupil size measured in the dark: Pre-op only

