**8. Is there a safety monitoring plan for this study?**

Yes  No

**9. Provide a summary of the statistical methods, data analysis, or data interpretation planned for this study. Factors for determining the proposed sample size (e.g., power) should be stated.**

Summary statistics will be calculated and used to describe the treatment groups (70 versus 110 degrees side-cut angles) in terms of all study variables: manifest refraction, corrected and uncorrected visual acuity and LASIK system used (FS200 or intralase). Statistics will be compiled for the one week, one month, three month, six month and 12 month time points post operatively. Paired t-tests will be used to analyze the difference of corrected and uncorrected visual acuity obtained by each group at the post-op time points, as well as the average change from pre-op to post op corrected and corrected visual acuities. In order to provide a statistically significant beta values, a N number of 200 patients will be needed.

IRB\_00074858

Created: 6/23/2014 8:21 PM

IRB\_00074858

PI: [name]

Submitted: 7/28/2014

View: 4.2 Consent Process

**Title:** 70 versus 110 Degrees Side-cut Angles in Femtosecond  
Laser-assisted in situ Keratomileusis

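### The planned paired t-test ignores which eye received which angle; blocking that right/left arrangement and analysing by it gives a small precision gain at almost no cost

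*Combined protocol and SAP*

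**What the plan says.** Four places bear on how angles reach eyes.

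- Study Purposes and Objectives (item 6): "One angle will be performed on the right eye and the other on the left eye". Neither angle is tied to a named side. The section gives reduced confounding as the reason for treating two eyes of one person.
- Study Information, item 1 (design): "Randomized Trial".
- Study Information, item 6 (procedures): patients leave the study if, on the day of surgery, "both eyes cannot be randomized and operated as per protocol". The same item says "All surgical procedures will be performed according to the surgeons' standard practices", and nothing fixes or records which eye is operated on first.
- Risks and Benefits, item 2: describes one angle in one eye and the other angle in the fellow eye, again without naming a side.

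On analysis, Study Information, item 9 says "Paired t-tests will be used to analyze the difference of corrected and uncorrected visual acuity obtained by each group at the post-op time points". It gives no term for eye side, arrangement or surgical order, and none of these is among the variables it lists for summary. On size it says only that "a N number of 200 patients will be needed".

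**The concern.** Pairing two eyes of one patient removes differences between patients. It does not remove systematic differences between the two eyes. Both eyes are tested at every visit, with uncorrected acuity read from a Snellen chart, and two eyes are normally operated on one after the other. A right-left difference is therefore plausible, for instance from surgical order or from letters remembered when the second eye is tested. Its size is unknown.

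When each patient receives both angles, the arrangement is the one feature that randomisation controls, and it is known for every patient. A plain paired t-test discards it. Two things follow. The right-left difference inflates the error term, and in any one trial a chance excess of one arrangement leaves part of that difference in the angle estimate. At stake is some precision in the main comparison, recoverable from data the trial will hold anyway.

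**Working it through.** **Inputs.** From the documents: 200 patients, hence 200 pairs, and a paired t-test. Assumed, because the documents give none: two-sided 0.05; SD of the between-eye difference within an arrangement σ = 0.10 logMAR (range 0.08 to 0.15); right-left difference δ = 0.01 to 0.02 logMAR, with 0.03 and 0.05 as larger cases; angle effect τ = 0.02 logMAR; all 200 pairs analysed.

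**The plan's own figure.** The 200 cannot be reproduced, since no effect size, SD, alpha or power is stated. Worked backwards at 80% power, 200 pairs detect (1.960 + 0.842)/√200 = 2.802/14.142 = 0.198 SD, which is 0.0198 logMAR at σ = 0.10. The assumed τ is close to that.

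**Model.** For patient i, let D be the 70-minus-110 difference and s = +1 if the right eye has 70 degrees, −1 otherwise. Then D = τ + sδ + e, with SD(e) = σ.

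**Plain test, simple 1:1 randomisation.** Var(D) = σ² + δ², an inflation of 1 + (δ/σ)². Power comes from the noncentral t on 199 df with noncentrality τ√200/√(σ² + δ²).

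| δ | Variance inflation | Noncentrality | Power, plain test |
|---|---|---|---|
| 0 | 1.00 | 2.828 | 0.804 |
| 0.01 | 1.01 | 2.814 | 0.800 |
| 0.02 | 1.04 | 2.773 | 0.788 |
| 0.03 | 1.09 | 2.709 | 0.769 |
| 0.05 | 1.25 | 2.530 | 0.711 |

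The analysis by arrangement stays at about 0.80 in every row (simulation). With the slightly smaller effect 0.0198, the plain test gives 0.796, 0.780 and 0.761 at δ = 0, 0.02 and 0.03. Intervals widen by √1.01 to √1.04, about 0.5% to 2%. Making up the loss with patients instead would take 200 × 1.04 = 208 pairs at δ = 0.02, or 200 × 1.09 = 218 at δ = 0.03.

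**Range of σ, at δ = 0.02.** At σ = 0.08 the inflation is (0.02/0.08)² = 6.25% and power goes from 0.940 to 0.927. At σ = 0.15 it is (0.02/0.15)² = 1.8% and power goes from 0.467 to 0.460.

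**Type I error of the plain test.** Under simple randomisation, simulation gives about 5% throughout. With the arrangements exactly balanced the test is conservative: 4.6% at δ = 0.02 and 2.9% at δ = 0.05. Blocking should therefore go together with the matching analysis.

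**Chance imbalance.** With Binomial(200, 0.5), the 95% range for one arrangement is 86 to 114. At 114:86 and δ = 0.02:

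- Shift in the estimate: (114 − 86)/200 × 0.02 = 0.0028 logMAR.
- In units of σ/√200 = 0.00707, the shift is 0.396.
- The test's own SD is √(0.01 + 0.0004 × (1 − 0.14²)) = 0.1019, so the critical value becomes 1.96 × 1.019 = 1.998.
- Rejection rate given that split: Φ(−1.602) + Φ(−2.394) = 0.055 + 0.008 = 6.3%. Simulations give 6.3% to 6.5%.

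**Why block as well.** At 114:86 the arrangement analysis has variance 200²/(4 × 114 × 86) = 1.02 times that of an even split. Blocking avoids this 2%.

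**The case against.** The strongest reply is that the planned test is not wrong. Under 1:1 randomisation, even unblocked, the paired t-test holds its 5% level and its estimate is unbiased in expectation. The 6.3% to 6.5% applies only to trials that happen to land at the edge of the 95% range, so it is chance error and not bias. Within 0.01 to 0.02 logMAR the loss is one to two points of power, and no document gives a side effect of any size. Item 9 also plans change from the pre-operative value, in which a stable testing-order effect would tend to cancel. All of this stands, and it is why the point is minor.

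A reader might infer more from the wording, in three ways.

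- **That the statements of assignment contradict each other.** They do not. The objectives name neither side, and with one angle per eye, randomising the eyes can only mean randomising the arrangement.
- **That every patient has the same angle on the same side**, so that angle and side are fully confounded. The randomised label and the day-of-surgery rule speak against this.
- **That a side term would cure every such problem.** It would not. If sides were fixed there would be one arrangement and nothing to compare, so only the allocation can prevent that. Nor does a side term remove a first-versus-second-eye effect unless surgical order follows side.

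**Conclusion.** The point holds as a free improvement of minor weight. The plan does not balance the arrangement, and its named test ignores it. That test remains valid under 1:1 randomisation but is somewhat less precise than it need be. With 200 pairs and an assumed SD of 0.10 logMAR, the variance cost is 1% to 4% for side effects of 0.01 to 0.02 logMAR and 9% for 0.03. The power cost at a 0.02 angle effect is about 0.4 to 1.6 percentage points (0.804 to 0.800 and 0.788), and 3.5 points at 0.03. These sizes rest wholly on assumed values. If the true side effect is near zero, the gain is near zero and almost nothing is lost. The documents do not support a finding that the planned comparison is biased or its error rate inflated.

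**What to change.** 1. **Allocation (Study Information, item 6).** State that each patient is randomised 1:1, in permuted blocks, to 70 right/110 left or 110 right/70 left.
2. **Analysis (item 9).** Replace the plain paired t-test with the comparison by arrangement: regress the 70-minus-110 difference on a side indicator coded +1/−1 and test the intercept. Keep that coding fixed; re-centring it at its sample mean would return the plain mean difference. Equivalently, take right-minus-left acuity, subtract its mean in one arrangement from its mean in the other (70-right minus 110-right), and halve the result: ((δ + τ) − (δ − τ))/2 = τ.
3. **Reporting.** Give the estimated right-left effect with its interval beside the angle effect.
4. **Data.** Record which eye was operated on first. If order does not follow side, the side term leaves an order effect in place and a separate order term would be needed.

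The cost is one sentence on allocation, a blocked list, one recorded item and one degree of freedom (198 left instead of 199). It needs no extra patients or visits.

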**7. Is this a multi-site study, where more than one site needs IRB approval?** Yes  No**8. Background and Introduction:**

Laser-assisted in Situ Keratomileusis has become the preferred corneal procedure to correct certain refractive errors. Technological advances have increased the accuracy and precision of current treatments. One of the major advancements in LASIK has been the introduction of Femtosecond Laser technology for flap creation. Several studies have compared microkeratome and femtosecond laser technology, showing superior accuracy and precision of flap dimensions in the latter.

The Femtosecond Laser technology provides different parameters and settings that can be changed according to the surgeon's preference. One of such parameters is the side-cut angle. Some of the most common side-cut angles used today include 45, 70, 90, and 110 degrees. Previous studies have reported on the visual outcomes of side-cut angles, but head to head comparisons are lacking. Currently, there are no studies comparing the safety and efficacy of the 70 and 110 side-cut angles in FS-LASIK. Information regarding the outcomes and complication rates between these side-cut angles will provide an objective measure that can be used when deciding which one is more suitable in FS-LASIK.

IRB\_00074858

Created: 6/23/2014 8:21 PM

IRB\_00074858

View: 2. Location and Sponsor

PI: [name]

Submitted: 7/28/2014

**Title:** 70 versus 110 Degrees Side-cut Angles in Femtosecond Laser-assisted in situ Keratomileusis

**a. Position of the Site Principal Investigator**

[Faculty or Non-Academic Equivalent](#)

**b. Will the Site PI consent participants?**  Yes  No

**6. Select HIPAA coverage for this study:**

Study procedures will be conducted within a HIPAA Covered Entity at this site (HIPAA Privacy Rule applies)

**7. Select the study procedures that will be conducted at this site:**

Recruitment

Consent/Enrollment

Research observation/intervention with participants

---

**Data collection**

---

**Data analysis**

**Do you have an enrollment goal or anticipated enrollment number for this site?**

- Yes
- No

8. **Select the University of Utah department responsible for this research:**

OPHTHALMOLOGY

9. **Add any additional sites that are part of this performance group**

There are no items to display

IRB\_00074858

Created: 6/23/2014 8:21 PM

IRB\_00074858

PI: [name]

Submitted: 7/28/2014

View: 3. Participants

**Title:** 70 versus 110 Degrees Side-cut Angles in Femtosecond  
Laser-assisted in situ Keratomileusis

### 3. Participants

**1. Ages of Participants:**

18 and older (Consent form needed)

**2. Specific age range of participants (e.g., 7-12 years old, 60+, etc.):**

21 years and older

**3. Indicate any vulnerable participant groups (other than children) included:**

None

**If 'Other', please specify:****If 'None' and no children are involved, answer the following question.****Has the participant selection process overprotected potential subjects who are considered vulnerable so that they are denied opportunities to participate in research?** Yes  No**4. Number of participants to be included and/or enrolled in this entire study, across all study locations:** 200**At Utah prior to October 2019:** 200**5. Characteristics of Participants/Inclusion Criteria:**

Subjects who are deemed suitable candidates for bilateral LASIK will be considered eligible for participation in this study. Correction will be distance for both eyes. Patients must be at least 21 years of age.

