**6. Participant Exclusion Criteria:**

Selection will be consistent with current standard of care. Any patient that is not a suitable candidate for LASIK will not be included.

**7. Is a substantial percentage of the participant population anticipated to be non-English speaking?** Yes  No

IRB\_00074858

Created: 6/23/2014 8:21 PM

IRB\_00074858

PI: [name]

Submitted: 7/28/2014

View: 4. Study Information

**Title:** 70 versus 110 Degrees Side-cut Angles in Femtosecond  
Laser-assisted in situ Keratomileusis

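### The unadjusted paired t-test of post-op uncorrected acuity carries any between-eye difference in pre-op best corrected acuity as noise; adjusting for that difference, already measured, would recover part of the lost precision

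*Combined protocol and SAP*

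**What the plan says.** All references are to the combined protocol and SAP.

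- **Inclusion** (3. Participants, item 5): "Subjects who are deemed suitable candidates for bilateral LASIK will be considered eligible for participation in this study". Two further conditions follow: "Correction will be distance for both eyes. Patients must be at least 21 years of age".
- **Exclusion** (3. Participants, item 6): "Selection will be consistent with current standard of care. Any patient that is not a suitable candidate for LASIK will not be included". No minimum best corrected acuity, maximum between-eye difference or amblyopia exclusion appears anywhere.
- **Design** (6. Study Purposes and Objectives): "One angle will be performed on the right eye and the other on the left eye". The stated reason is: "By performing different side-cut angles on a same individual will allow a direct comparison of outcomes, minimizing confounding variables".
- **Allocation** (4. Study Information, items 1 and 6): the trial is described as randomised, and a patient is discontinued if, on the day of surgery, "both eyes cannot be randomized and operated as per protocol".
- **Measurements** (4. Study Information, item 6): best corrected acuity is taken pre-op and at months 3, 6 and 12. Uncorrected acuity is taken pre-op and at every post-op visit. Both eyes are assessed.
- **Analysis** (4. Study Information, item 9): "Paired t-tests will be used to analyze the difference of corrected and uncorrected visual acuity obtained by each group at the post-op time points". The same sentence adds tests of average change from pre-op, but it names corrected acuity twice and uncorrected acuity not at all. No covariate is planned.

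**The concern.** A within-patient comparison is most precise when the two eyes would see equally well apart from the treatment. The eligibility items ask whether the patient can have the operation, not whether the eyes are alike. If one eye has reduced best corrected acuity, its uncorrected acuity after surgery can hardly be better than that eye's potential, whichever angle was cut. Such a patient contributes a between-eye difference that has nothing to do with the angle.

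At stake is the width of the confidence interval for uncorrected acuity. The plan states no effect size, SD or power, so it shows no margin that could absorb a loss of precision. The information needed to reduce the loss, pre-op best corrected acuity in each eye, is collected but not used in the comparison.

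**Working it through.** **1. The plan's own figure.** Item 9 gives 200 patients without alpha, power, effect size or SD, so it cannot be reproduced. Solving n = ((z for alpha + z for power) / (delta/SD))² backwards at an assumed two-sided 5% and 80% power gives delta/SD = (1.960 + 0.842)/√200 = 0.198.

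**2. Extra variance.** Let s be the SD of the paired difference in patients with symmetric eyes, p the share of patients with one limited eye, and d the deficit. With eyes randomised, the deficit has random sign, so it adds nothing to the expected mean difference and p·d² to the variance:

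- SD = √(s² + p·d²)
- effective N = 200·s² / (s² + p·d²)

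None of s, p or d is in the documents. Assumed ranges: s 0.08 to 0.15 logMAR, p 1% to 4% (2 to 8 of 200 patients), d 0.2 to 0.3 logMAR.

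| Case | s | p | d | s² + p·d² | SD | Rise | Effective N |
|---|---|---|---|---|---|---|---|
| Most favourable | 0.15 | 1% | 0.2 | 0.0225 + 0.0004 | 0.151 | 1% | 197 |
| Midpoints | 0.115 | 2.5% | 0.25 | 0.01323 + 0.00156 | 0.122 | 6% | 179 |
| Least favourable | 0.08 | 4% | 0.3 | 0.0064 + 0.0036 | 0.100 | 25% | 128 |

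If 200 symmetric pairs gave 80% power, power becomes Φ(2.802·√(effective N/200) − 1.960): about 79%, 75% and 61% in the three rows.

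**3. Does change from pre-op remove it?**

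- *Corrected acuity:* yes. The fixed difference is in both the pre-op and post-op values and cancels. In simulation the SD of the change difference stayed at about 0.100 in every scenario.
- *Uncorrected acuity:* item 9 as written names no such test. If one was meant, the fixed difference would cancel under a simple additive model, but between-eye differences in pre-op refractive blur would enter. With s = 0.10 and an assumed blur SD of 0.1 to 0.3 logMAR, the SD is √(0.10² + 0.1²) = 0.14 to √(0.10² + 0.3²) = 0.32. The post-op test has 0.10 to 0.12 in the simulated scenarios.

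**4. What adjustment recovers.** Pre-op best corrected acuity is measured with error. With an assumed measurement SD of 0.05 logMAR per eye, the error variance of the between-eye difference is 2 × 0.05² = 0.005. The share of the extra variance removed by linear adjustment is p·d² / (p·d² + 0.005).

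- *p = 5%, d = 0.3, s = 0.10* (beyond the range above, used to show the mechanism): share 0.0045/0.0095 = 0.47. The residual SD is √(0.01 + 0.53 × 0.0045) = 0.111, against 0.120 unadjusted and 0.100 without such patients. Simulation gave 0.111, 0.121 and 0.100.
- *Midpoints:* share 0.00156/0.00656 = 0.24. The residual variance is 0.01323 + 0.76 × 0.00156 = 0.01442, so effective N rises from about 179 to about 183.

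The better the pre-op measurement, the larger the share recovered.

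**The case against.** The strongest reply is that the affected patients may hardly exist in this trial. Selection follows standard of care, and the documents do not say how that treats an amblyopic or otherwise limited eye. This stands: the number admitted could be near zero, and every input to the size is an assumption.

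A second reply is that randomising the eyes already deals with the imbalance. It does so for bias. A reader might infer that the angle comparison is confounded, or that the protocol's claim for the same-patient design fails. The documents do not support that, because noise of random sign is not confounding. That a few such patients could shift the mean in one trial is the wider confidence interval described another way, not a second harm. What randomisation does not do is restore the lost precision.

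A third reply is that broad eligibility is a legitimate choice. This also stands. A reader might infer that patients with unequal eyes must be excluded. But the trial also evaluates complications, which do not depend on equal visual potential. Exclusion would discard those data and narrow the population, and a blanket bar on amblyopia would also remove patients whose eyes are equally limited and add no between-eye difference.

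**Conclusion.** The point holds as a matter of precision for one family of tests, the unadjusted paired comparisons of post-op uncorrected acuity. It does not extend to change in corrected acuity, where the difference cancels, and it is not a bias.

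The size is unknown from the documents. Under the assumed ranges the SD rises by 1% to 25%, about 6% at the midpoints, with an effective N of about 179 of 200. A reader might take the lower end, 128, as the expected loss, but it needs the least favourable value of all three inputs at once. With standard-of-care selection the loss may be negligible.

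The case for acting rests less on the size than on the cost: a baseline value already measured in both eyes can be used to make the comparison more precise.

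**What to change.** In 4. Study Information, item 9, make the main analysis of post-op uncorrected acuity at each time point a linear model on the within-patient difference:

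(post-op uncorrected acuity, 70 minus 110 degrees) = a + b × (pre-op best corrected acuity, 70 minus 110 degrees) + error.

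The intercept a, taken at a pre-op difference of zero, is the angle effect and is the quantity to test and report with its confidence interval. The covariate should not be centred at its sample mean, since the intercept would then simply return the unadjusted mean difference. Keep the unadjusted paired t-test as a sensitivity analysis. In the same item, state whether change from pre-op is to be tested for uncorrected acuity, since the sentence now names corrected acuity twice.

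The cost is one degree of freedom and a revised sentence, with no new measurement. The gain is partial: on the assumptions above, about a quarter of the extra variance at the midpoints and about half when limited eyes are more frequent and more affected.

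A limit on the between-eye difference in pre-op best corrected acuity could be added to the eligibility items if the sponsor wants it. It is optional, because of what it gives up in population and complication data.
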